7.1.2.3. Hypothesis: Albuterol Use Will Increase Several Days Prior to a CAE

The hypothesis under consideration is that albuterol use will increase several days prior to a CAE. Several days will be defined as 7 days prior to the date of the CAE symptom peak for this analysis.

For each subject that experiences at least 1 CAE, Y_1, \dots, Y_7 will represent the number of puffs of albuterol during the 7 days preceding the date of the CAE symptom peak and let Y_8, \dots, Y_{14} will represent the number of puffs taken each day during day 8 through 14 preceding the date of the CAE symptom peak. Under the hypothesis of no increased albuterol use preceding an exacerbation (ie, null hypothesis) assume for subject “xxx” that $Y_i \stackrel{iid}{\sim} Poisson(\lambda_{xxx})$ for all subjects i . Alternatively, if albuterol use does increase prior to an exacerbation, then

$Y_i \stackrel{iid}{\sim} \text{Poisson}(\lambda_{xxx})$ during day 8 through 14 preceding the date of the CAE symptom peak and $Y_i \stackrel{iid}{\sim} \text{Poisson}(\lambda_{xxx} + \delta)$ for the immediate 7 days preceding the CAE(s). Also, for random subject effect, assume λ_{xxx} follows some distribution to account for subject to subject variability. Let d_{xxx} will equal to the mean number of puffs during the 7 days immediately preceding the date of the CAE symptom peak minus mean number of puffs during days 8 through 14 preceding the date of the CAE symptom peak. To assess if albuterol usage increases 7 days prior to a CAE, $H_0: \mu_D = 0$, $H_1: \mu_D > 0$ will be tested using a t-test at the 0.05 significance level.

7.1.2.4. Number of Days Prior to the Peak of a CAE When Albuterol Use Increased

Among patients who experienced a CAE, summary statistics of the number of days prior to the peak of a CAE when albuterol use increased will be presented overall and by moderate CAEs and severe CAEs for 3 thresholds defining an increase in albuterol use;

- (i) First occurrence of a single day's albuterol use exceeding 4 inhalations;
- (ii) First occurrence of a single day's albuterol use exceeding 12 inhalations;
- (iii) First occurrence of a single day's albuterol use exceeding 20 inhalations.

Among patients who did not experience a CAE, summary statistics, including 95% CIs, of the proportion of eMDPI time on study days when a patient exceeded a given threshold of albuterol use (number of days a given patient's single day's albuterol use exceeded 4 inhalations / total number of eMDPI study days for a given patient) will be summarized for 3 thresholds defining an increase in albuterol use;

- (i) a single day's albuterol use exceeding 4 inhalations;
- (ii) a single day's albuterol use exceeding 12 inhalations;
- (iii) a single day's albuterol use exceeding 20 inhalations.

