Recurrent Clinical Asthma Exacerbation Rate: The percentage of patients who experience more than 1 moderate or severe CAE at the end of study follow-up.

Time to Clinical Asthma Exacerbation: Time, in days, from Study Day 1 to the Date of Symptom Peak plus 1.

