7.5.2.1. Within Patient CAE Analyses

For each CAE event occurring at least 2 weeks after baseline, device-use measures (albuterol use, inhalational flow [MIF], inhalational volume, and time to MIF) will be summarized for each of 2 weeks of interest: first- 'CAE-adjacent week', the week immediately preceding the onset of CAE symptom (ie, day 1 through 7 preceding the date of the CAE symptom onset), and second – 'CAE-Prior Adjacent week', the week preceding that week (ie, during day 8 through 14 preceding the date of the CAE symptom onset). Summary measures of daily and or weekly use will be compared between the two weeks, as proposed below:

Albuterol use measures:

- total number of inhalations in that week
- the maximal daily number of inhalations in that week
- the mean number of daily inhalations (ie, total number of inhalations divided by number of days with number>0)
- occurrence of a single day's albuterol use exceeding 4 inhalations;
- occurrence of a single day's albuterol use exceeding 8 inhalations
- occurrence of a single day's albuterol use exceeding 12 inhalations
- number of days when albuterol use exceeding 4 inhalations;
- number of days when albuterol use exceeding 8 inhalations
- number of days when albuterol use exceeding 12 inhalations

To note, in this analysis, no inhalation in any day will be taken as a 0 count.

Inhalation flow values parameters:

- maximal daily MIF during the week
- minimal daily time to MIF within a week
- maximal total daily inhalational volume within a week,

To note, if no inhalation was taken at a specific day, flow value parameters will be missing and will not be imputed.

Analysis will be based on all patients CAEs for which there are 14 days (or more) prior to the CAE onset, where patient has been on study and CAE free.

Descriptive statistics of use measures in the 'CAE-adjacent week' and 'CAE-Prior Adjacent week' will be presented.

Continuous measures will be compared between the 2 weeks using paired t-test (and Wilcoxon Signed Ranks test) whereas binary patterns will be compared using Mc-Nemar test.

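### SAP 7.1.2.3 words its t-test as showing a rise in albuterol use before a CAE but counts back from symptom peak, and the SAP does not name the onset-based comparison in 7.5.2.1 as the answer to the early-warning hypothesis

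*SAP*

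**What the plan says.** SAP 1.1 gives the study hypothesis: use rises several days before a severe CAE and can mark deterioration. SAP 7.1.2.3 carries a test under that label, for any CAE. It defines the window as "Several days will be defined as 7 days prior to the date of the CAE symptom peak for this analysis", takes d as mean daily puffs on days 1-7 before peak minus mean daily puffs on days 8-14 before peak, and runs a one-sided t-test at 0.05. The purpose is worded without the peak: "To assess if albuterol usage increases 7 days prior to a CAE". The unit is the patient ("For each subject that experiences at least 1 CAE"), with no rule on which CAE supplies d when there are several.

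SAP 7.5.2.1 compares the same pair of weeks counted from a different date: "day 1 through 7 preceding the date of the CAE symptom onset", against the week before that. On the CAEs that enter it says: "Analysis will be based on all patients CAEs for which there are 14 days (or more) prior to the CAE onset", with the patient on study and CAE-free throughout. The test: "Continuous measures will be compared between the 2 weeks using paired t-test", with a signed-rank test alongside and McNemar for binary measures. Sidedness is not given. SAP 7.5.2 introduces these as several analyses proposed to study correlations; none is named as the test of the hypothesis.

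**The concern.** If symptoms begin some days before they peak, reliever use taken to treat them falls inside the week that 7.1.2.3 calls prior to the CAE. A significant result then cannot separate an early-warning rise from treatment of symptoms already under way. Protocol 3.3 wants changes that identify at-risk patients who could then receive an intervention, so the difference bears on what the trial can claim. The comparison that does address a rise before symptoms is in 7.5.2.1. If the two results disagree, nothing in the SAP says which one answers the hypothesis.

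A linked gap is that 7.5.2.1 puts every eligible CAE of a patient into ordinary paired tests, with no patient term.

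**Working it through.** **The plan's own figures.** 400 x 0.90 = 360 evaluable. 360 x 0.20 = 72 and 360 x 0.25 = 90 CAEs. 360 x 0.067 = 24.1 moderate and 360 x 0.15 = 54 severe, about 78 together. All reproduce. The documents give no power calculation for the 7.1.2.3 test.

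**The two comparisons.**

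| | SAP 7.1.2.3 | SAP 7.5.2.1 |
|---|---|---|
| Counted back from | symptom peak | symptom onset |
| Weeks | days 1-7 v 8-14 | days 1-7 v 8-14 |
| Unit | patient, CAE not specified | every eligible CAE |
| Test | one-sided t, 0.05 | paired t, sidedness not stated |
| Labelled as the hypothesis | yes | no |

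**Usable n.** Section 7.1.2.3 needs days 8-14 before peak, so a CAE peaking in the first two weeks lacks a full comparison week. Assuming CAEs are spread evenly over 84 days, 70/84 remain: 72 x 70/84 = 60 and 90 x 70/84 = 75.

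**Expected difference when nothing rises before onset.** With lag L days from onset to peak and use multiplied by m in that interval only, E(d) = mean use x (m - 1) x L / 7. The mean of 5.5 per day (SD 9.7) is the exacerbating group's in the nested cohort described in Protocol 3.3. L and m are assumptions.

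| Lag (days) | m = 1.5 | m = 2 |
|---|---|---|
| 0 | 0 | 0 |
| 1 | 0.39 | 0.79 |
| 2 | 0.79 | 1.57 |
| 3 | 1.18 | 2.36 |

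**How often the test is significant.** Simulation: patient rates gamma with shape (5.5/9.7)^2 = 0.3215 and scale 5.5/0.3215 = 17.11; independent daily counts, negative binomial with size 0.5 to 2 (assumed scatter); one-sided t-test at 0.05.

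| Lag (days) | Use doubled, n = 60-75 | 1.5-fold rise, n = 72-90 |
|---|---|---|
| 0 | about 5% | 4-5% |
| 1 | 16-45% | 10-21% |
| 2 | 35-85% | 19-50% |
| 3 | 57-98% | 31-76% |

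The right-hand column uses the full expected number of CAEs; at 60-75 it would be somewhat lower. Under the SAP's own Poisson model at n = 72-90, with a 1.5-fold to 2-fold rise, the rates are 79-100% at 1 day and about 100% at 2 to 3 days. Counted back from onset, with the same absence of any rise before onset, the rate is 4.7-5.3%.

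**Equivalence of the two tests once both start at onset.** Section 7.5.2.1 states: "in this analysis, no inhalation in any day will be taken as a 0 count". The weekly total is therefore 7 x the daily mean, the paired difference in totals is 7d, and the t statistic does not change with scale. On the same CAEs an onset-based 7.1.2.3 and the 7.5.2.1 weekly-total t-test are the same test. This does not apply to the mean daily measure in 7.5.2.1, which divides by days with use only.

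**Repeat CAEs in 7.5.2.1.** With independent daily counts and no patient-specific response, the patient's level cancels from each difference and differences from separate windows are uncorrelated. Simulation with 60 patients, 10% or 30% having a second CAE, gives 3.6-5.1% rejection at a nominal two-sided 5%, so no inflation. With an assumed within-patient correlation rho of 0.2-0.8 and 10-30% having a second CAE, it gives 5.6-9.6%; using only first CAEs, 4.8-5.4%. A check by the design effect 1 + rho x (sum m^2 / sum m - 1), where m is now the number of CAEs per patient, with 78 patients, 23 of them having two CAEs, and rho 0.8: sum m = 101, sum m^2 = 55 + 92 = 147, design effect 1.36, rejection 9.3%.

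**The case against.** The peak anchor is stated in the sentence after the hypothesis and d is written out in full, so nothing is hidden. Peak is also a deliberate choice elsewhere: Protocol 6.1.2 uses it for the first two albuterol parameters, and SAP 7.5.1 defines time to CAE as "Time, in days, from Study Day 1 to the Date of Symptom Peak plus 1". On that footing, before a CAE could be read as before its peak. Protocol 3.3 also reports that symptoms and rescue use rose together in an earlier diary-card study, so a symptom-driven rise could still be a marker of deterioration. The study is exploratory, ranks no endpoints, and calls a different hypothesis (more than 12 inhalations) primary in Protocol 9.5.2.1. The daily-window summaries in SAP 7.1.2.2 would help show whether a rise is confined to the last days.

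Much of this stands. A reader might infer that the anchor is a slip, that the SAP has no onset-based analysis, or that the percentages above are false-positive rates. The documents support none of these. The true mean of d is positive in those simulations, so the percentages are power to detect a real rise before peak. Nor do the documents show that the paired tests in 7.5.2.1 are too liberal; that needs patients to differ in their response, for which no figure is given.

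What the objection does not remove is that 7.5.2.1 treats onset as a separate date, and that the label on 7.1.2.3 is broader than its window.

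**Conclusion.** The point holds as a mismatch between wording and window, and should be fixed. The labelled test shows a rise before symptom peak. Reporting it as a rise before a CAE, in support of early warning, would overstate it if symptoms precede peak by a day or more. How often that would happen rests on an assumed lag, rise and scatter: never at zero lag, and in roughly one trial in six to nearly all of them across lags of 1 to 3 days with doubled use. The onset-based analysis already exists and lacks only a stated role.

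The repeat-CAE gap is smaller and conditional: rejection of about 5-10% at a nominal 5% under the assumed correlations, and no inflation without them. The missing rule on which CAE supplies d in 7.1.2.3 is a point of clarity only. No planning figure is wrong.

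**What to change.** Do one of two things.

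- **Wording (lighter).** In the title and conclusion of SAP 7.1.2.3 say *before symptom peak*, and name the 7.5.2.1 weekly-total comparison, with its sidedness, as the test of the hypothesis. No CAEs are lost, because 7.5.2.1 already has its 14-day condition.
- **Anchor.** Count both weeks in 7.1.2.3 back from symptom onset, with the 14 CAE-free days of 7.5.2.1. This needs some programming, but the onset date is already used in 7.5.2.1. The extra loss is small because 7.1.2.3 already needs 14 days before peak: under even timing it is lag/84 of CAEs, so at 3 days 72 x 3/84 = 2.6 to 90 x 3/84 = 3.2, apart from any repeat CAEs dropped by the CAE-free condition.

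In 7.5.2.1, use the first eligible CAE per patient or a patient-clustered analysis. The first-CAE rule sets aside 6 to 18 second CAEs if 10-30% of 60 patients have one; clustering keeps them. In 7.1.2.3, state that d comes from the first eligible CAE. The peak-anchored descriptions in 7.1.2.2 and 7.1.2.4, and time to CAE, stay as they are. Sample size, visits and data collection do not change.

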6.1.2. Albuterol Use

Albuterol usage data will be downloaded using extraction software directly from eMDPI devices collected from the patients at their final study visit after return of the device to the depot.

For albuterol use, parameters of interest will include (1) the total number of inhalations in the days preceding the peak of a severe CAE, (2) the number of days prior to the peak of a severe CAE when albuterol use increased, (3) the number of albuterol uses in the 24 hours preceding a severe CAE.

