4. GENERAL ISSUES FOR DATA ANALYSIS

4.1. General

Descriptive statistics for continuous variables include n (number), mean, standard deviation (SD), median, minimum, and maximum. Minimum and maximum will have the same number of decimal points as the original data. Mean and median will have 1 more decimal point than the original data. Reporting of SD will have 2 more decimal points than the original data.

Descriptive statistics for categorical variables include patient counts and/or counts and percentages. Categories for missing data will be presented, if necessary. Confidence intervals (CIs) of means and/or proportions will be reported as specified. Summaries will be provided overall and by CAE status (CAE: No, CAE: Yes, All) and by CAE severity (Yes: Moderate, Yes: Severe) where appropriate.

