7.1.1. Albuterol Use Definition

Baseline albuterol use is defined as no more than 4 inhalations (eg, 0 to 4 inhalations) per day of use regardless of the number of days albuterol is used in a 7-day period.

Daily baseline albuterol use is defined as no more than 4 inhalations (eg, 0 to 4 inhalations) per day.

Week 1 Patient Albuterol Use: Week 1 patient albuterol use is each patient's total number of albuterol inhalations taken and the number of days used during the first week (study day 1 through study day 7) of study participation with an indicator of whether or not any daily usage of albuterol exceeded 4 inhalations. It is presented as WK1:I#iD#dMT4Y/N, where "i" is the number of albuterol inhalations and "d" is the number of days used in the first 7 days of the study, and "MT4Y/N" is an indicator of whether or not any of the days albuterol was used exceeded 4 inhalations. For example, "I28D7MT4N" indicates a total of 28 inhalations were taken, albuterol use was used each day and none of the daily number of inhalations exceeded 4 (No More Than 4 inhalations per day Yes/ No).

Week 2 Patient Albuterol Use: Week 2 patient albuterol use is each patient's total number of albuterol inhalations taken and the number days used during the second week (study day 8 through study day 14) of study participation with an indicator of whether or not any daily usage of albuterol exceeded 4 inhalations. It is presented as "WK2:I#iD#dMT4Y/N", where "i" is the number of albuterol inhalations and "d" is the number of days used in the second week of study.

Albuterol use will be examined by the following 3 parameters; (i) total number of inhalations in the days preceding the peak of a CAE, (ii) number of days prior to the peak of a CAE when albuterol use increased, and (iii) number of albuterol uses in the day preceding a CAE.

The maximum number of inhalations taken within a 24-hour period by each patient: The date and time stamp of the inhalations are taken into consideration when determining the maximum number of inhalations taken within a 24-hour period by each patient. For patients who experienced a CAE, the maximum number of inhalations taken within a 24-hour period is determined among the days prior to the date of the symptom peak of the exacerbation.

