7.1.2. Analysis Methods for Albuterol Use

7.1.2.1. Pattern of Baseline Daily and Weekly Albuterol Use

Summary statistics including 95% CIs of the proportion of eMDPI time on study days when a patient took 0 to 4 inhalations a day (number of days a given patient took 0 to 4 inhalations a day divided by the total number of eMDPI study days for a given patient) will be summarized overall and by CAE status and by CAE severity. In addition, the proportion of patients exhibiting

weekly baseline albuterol use (Week 1, Week 2, ..., Week 12) will be summarized overall and by CAE status and by CAE severity.

Week 1 and Week 2 patient albuterol use patterns, “WK1:I#iD#dMT4Y/N” and “WK2:I#iD#dMT4Y/N” designation, will be summarized descriptively (counts and percent) overall and by CAE status and by CAE severity.

7.1.2.2. Total Number of Inhalations in the Days Preceding the Peak of a CAE

For patients who experienced a CAE, summary descriptive statistics of the total number of inhalations taken in 1 day (eg, the 24-hour period on the day prior to the date of the CAE symptom peak) and at 3, 5, 7, 10, 14, and 21 days preceding the date of the CAE symptom peak will be presented overall and by moderate CAEs and severe CAEs.

In this analysis, among patients experiencing more than 1 CAE, the subsequent CAEs can be considered a separate CAE distinct from the first (preceding) CAE provided the patient exhibited at least 1 day of baseline albuterol use after the first (preceding) CAE’s date of symptom peak and prior to the subsequent CAE’s date of symptom peak. For patients who experience multiple CAEs (eg, 3), for a given number of days preceding a CAE (eg, 21 days), if the (eg, third) CAE overlaps with the time period of the preceding (eg, second) CAE, the CAE (eg, third CAE) should not be included in the analysis.

Mean and 95% CI of the total number of inhalations per day for each eMDPI study day will be summarized graphically. The number of patients contributing to the summary statistic at study at Day 7, 14, 21, 28, 35, 42, 49, 56, 63, 70, 77, and 84 will also be presented. Three line graphs will be presented in 1 figure: “Overall” and by “CAE Status” (Yes, No). Three line graphs will be presented in a second figure; “CAE Status No”, “CAE Status Yes: Severe” and “CAE Status Yes: Moderate”.

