7.5.2.2. Time to Clinical Asthma Exacerbations Short-term Exacerbation Risk (7 days)

For each patient, the following 3 landmark use events will be identified:

- first time in study when had >4 inhalations per day ("low use group")
- first time in study when had >8 inhalations per day ("medium use group")
- first time in study when had >12 inhalations per day ("high use group").

A patient may be included in more than 1 landmark use group (for example, if had >12 inhalations a day any time during study, then on that time or already before he/she also had >8 and >4 a day).

For each landmark use groups, time to CAE within 7 days since the landmark event will be estimated and plotted using Kaplan-Meier plot. The 3 groups will be presented in the same plot, to assess a possible 'dose-response' association, if higher use is associated with shorter time to CAE.

If a CAE has not occurred within 7 days, then that observation will be censored at 7 days or earlier if follow-up had completed/terminated before 7 days elapsed. Note, if CAE occurred on the same date where landmark use happened, then time to CAE will be calculated as 0.

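### SAP 7.1.2.4 dates the pre-exacerbation rise in albuterol use from the first day over a threshold, with no look-back limit, prior-day condition or repeat-CAE rule, so read literally an early or habitual high-use day sets the lead time

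*SAP*

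**What the plan says.** Protocol 2.1 and 6.1.2 name three albuterol parameters of interest. The second is "the number of days prior to the peak of a severe CAE when albuterol use increased". SAP 7.1.2.4 is the output labelled as reporting it, for all CAEs and by severity. It defines the increase in three ways, the first being "First occurrence of a single day's albuterol use exceeding 4 inhalations"; the other two replace 4 by 12 and 20.

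Nearby sections are more specific:

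- SAP 7.1.1: "Daily baseline albuterol use is defined as no more than 4 inhalations" per day. This is a fixed value, not the patient's own level.
- SAP 7.1.2.2 counts inhalations on the day before the peak and "at 3, 5, 7, 10, 14, and 21 days preceding the date of the CAE symptom peak". Its rule for repeat events begins "In this analysis, among patients experiencing more than 1 CAE, the subsequent CAEs can be considered a separate CAE". The same rule, with the same limiting opening, appears in 7.2.2.1 and 7.3.2.1 but not in 7.1.2.4.
- SAP 7.5.2.2 uses a similar event, worded "first time in study when had >4 inhalations per day", but stops follow-up at 7 days.
- For patients without a CAE, 7.1.2.4 reports something else: "Among patients who did not experience a CAE, summary statistics, including 95% CIs, of the proportion of eMDPI time on study days" on which the threshold was exceeded.
- SAP 4.1: "Descriptive statistics for continuous variables include n (number), mean, standard deviation (SD), median, minimum, and maximum". The lead time will therefore be shown with its mean, SD and maximum as well as its median.

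**The concern.** A lead time needs a defined starting point. Here it is the first day over a fixed count, and nothing ties that day to the coming exacerbation. A patient who habitually uses more than 4 inhalations crosses on study day 1 or 2, and a low user may have one isolated high day weeks before any deterioration. In both cases the result largely measures how long the patient had been on study when the CAE peaked.

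The trial enrols uncontrolled patients (ACQ-5 of at least 1.5). In the earlier electronic-monitoring study cited in Protocol 3.3, patients who went on to exacerbate averaged 5.5 actuations a day, already above the lowest threshold.

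Readers will take this number as the warning time before an exacerbation. They will set it against the older study in Protocol 3.3, where changes were seen from 10 days before the event and were well established by 5 days.

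**Working it through.** **Plan figures.** Section 7.1.2.4 states no figure of its own. The planned event count, used below only to size the window loss, reproduces: 400 × 0.90 = 360 evaluable patients; 360 × 0.20 = 72 and 360 × 0.25 = 90 CAEs.

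**Step 1: constant use, Poisson daily counts.** P(day > 4) = 1 − Σ(k = 0 to 4) e^(−λ) λ^k / k!.

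- λ = 1.83 a day (mean of non-exacerbators, Protocol 3.3): P = 0.0386. P(at least one such day in 84) = 1 − (1 − 0.0386)^84 = 0.96.
- λ = 5.5 a day (mean of exacerbators): P = 0.642, so the first crossing falls on average on day 1/0.642 = 1.6. With the peak uniform on study days 15–84 (mean 49.5), the mean lead is 49.5 − 1.6 = 47.9 days, with no deterioration at all.

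**Step 2: simulation.** 60,000 patients per setting.

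- From Protocol 3.3: mean (SD) daily use of 5.5 (9.7) or 1.83 (3.3).
- Assumed: those SDs are between-patient; patient means follow a gamma distribution; daily counts are Poisson, either plain or with a gamma day-to-day multiplier of shape 1 (four settings in all); the peak is uniform on days 15–84; the rise, when present, is +6 a day over the last 5 or 10 days before the peak.
- Current rule: first day over threshold from day 1 to the day before the peak.
- Proposed rule: first day over threshold that follows a day at or below it, both within the 14 days before the peak.

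Results at the threshold of 4, among those who cross (ranges over the four settings):

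| Truth | Current rule | Proposed rule, 14 days |
|---|---|---|
| Flat use | median 42–45 days; R² with peak study day 0.7–0.8 | median 9–11; 22–51% of CAEs have a crossing |
| 5-day rise | mean 17–29; 30–56% over 14 days; median 5–10 in three settings, about 21 in the fourth | median 5 in all four; at least 80% have a crossing |
| 10-day rise | mean 21–30; median 10 in three settings, 20–21 in the fourth | median 10 in all four; at least 77% have a crossing |

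Under flat use and the current rule, 41–68% never exceed 4, 59–92% never exceed 12 and 69–98% never exceed 20. Section 7.1.2.4 does not say how these patients are reported.

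**Step 3: thresholds of 12 and 20.** Here the proposed rule's medians depend on whether the day-to-day multiplier also scales the rise. If it does, a 5-day rise reads 4–5 days at 12 and 4–6 at 20. If the rise is simply added, at 5.5 a day with the multiplier it reads 9 and 10.

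**Step 4: repeat CAEs, illustration.** If the first day over 4 is study day 3 and peaks fall on days 30 and 70, per-event counting gives 30 − 3 = 27 and 70 − 3 = 67 days, both set by the same day.

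**Step 5: CAEs without a full window.** If peaks were uniform over days 1–84, 14/84 = 17% lack 14 earlier days (72 × 14/84 = 12; 90 × 14/84 = 15). For 21 days it is 21/84 = 25% (18 to about 23).

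**The case against.** **The reading.** 7.1.2.4 does not itself say first in study; that phrase is in 7.5.2.2, which Amendment 01 rewrote for other reasons. The section speaks of patients with a CAE, which also fits one value per patient, and then the two-lead example disappears. This stands: the text permits the repeat-CAE problem but does not require it, and the documents do not say how many patients would have more than one CAE. It does not rescue the definition, because no passage supplies another start to the search.

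**Other evidence on timing.** A reader might infer that the lead time has no comparator at all, or that the SAP has nothing else on timing. The documents do not support that. 7.1.2.4 gives the background frequency of threshold days in CAE-free patients. 7.5.2.2 follows everyone who crosses, with or without a CAE. 7.5.2.1 compares adjacent weeks, and the graded windows of 7.1.2.2 show roughly when use climbs. These are indirect, but they exist.

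**The size.** The starkest figures assume no rise. With a true rise, the current median is close to correct in three of four settings; it is the mean, SD and maximum that suffer.

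**The remedy.** A window with an upward crossing does not cure habitual use. For a patient fixed at 5.5 a day, a variant that lets the prior day fall just before the window still gives a median of 12 days, with or without a 7-day rise. Flat use at 9–11 days also looks like a 10-day run-up. Both points stand, and they are why the lead time must be read with the share of CAEs that cross.

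**Conclusion.** The point holds as a defect of definition in one descriptive output. Applied literally, 7.1.2.4 gives a lead time driven largely by time on study when use is flat, and an inflated mean when use does rise. The omissions can be read directly from the text. The sizes rest on the assumed gamma-Poisson use, uniform peak timing and rise of 6 a day; only the means and SDs and the 5–10 day timing come from the protocol.

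A reader might go further and infer that the trial's hypothesis test is compromised. It is not: 7.1.2.3 compares days 1–7 with days 8–14 before the peak and does not use this definition. No alpha, power or sample size depends on 7.1.2.4. Nor should the proposed rule be credited with recovering the timing of a rise at 12 or 20 inhalations; it does so reliably only at 4. The point is worth fixing because the protocol names this parameter and 7.1.2.4 is the only output labelled as reporting it.

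**What to change.** Amend SAP 7.1.2.4, keeping the peak as anchor:

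1. Search only the 14 days before the date of symptom peak, with a 21-day version alongside. Both lengths are already used in 7.1.2.2.
2. Define the increase as the first day over threshold that follows a day at or below it, both inside the window.
3. State that the repeat-CAE rule of 7.1.2.2 applies, with the same window.
4. With every lead time, report the share of CAEs with no crossing, the share above threshold throughout the window, and the number without a full window. State that the median is not to be interpreted alone.

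Optionally, compute the same quantities in CAE-free patients on matched index days.

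The cost is SAP wording and minor reprogramming. Reported lead times will be shorter. Run-ups longer than 13 days (20 in the 21-day version) cannot be seen. CAEs peaking before study day 15 (22) lack a full window. Patients above threshold throughout get no lead time and are counted separately (0–23% at the threshold of 4 in the simulation). In the 21-day version at that threshold the median is 5–10 days for the 5-day rise, 10 for the 10-day rise and 17–18 for flat use, so the same caution applies.
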